and continue HIV and TB care.²⁵ Other work by our team has also shown that PLWH with depression and/or SU²⁶ report lack of respect and stigma from CHWs as a barrier to accessing care.²⁷ There is also quantitative evidence that PLWH experience high levels of stigma related to MH – and particularly to SU – that contributes to delays in seeking or re-starting care.²⁸ Further, there is evidence that when CHWs have negative attitudes towards patients with depression or SU, they spend less time with these patients, are less likely to implement evidence-based practices, and deliver less patient-centred care.²⁹ At the same time, it is well documented that MH and SU stigma lead to negative health outcomes among patients including patient delays in seeking treatment, lower treatment continuation rates, and poorer physical health.^{30–32} In SA specifically, patients have been found to stop seeking TB/HIV care or terminate prematurely due to stigmatisation of MH-related symptoms.³³ Yet, to date, few studies have explored how to reduce CHW stigma as a means to improve re-engagement in TB/HIV care.

There is evidence that MH-related stigma reduction interventions in low and middle-income countries (LMICs) can reduce discrimination and improve patient outcomes. In SSA, stigma reduction strategies for TB and HIV stigma have demonstrated efficacy for reducing discriminatory practices among health workers and improve patient-level outcomes, including engagement in TB and HIV care.^{34–37} However, compared to TB- and HIV-related stigma, there is much less research on how to shift MH and SU-related stigma in LMICs, particularly in the context of TB/HIV care. The limited evidence available indicates that the most effective MH-related stigma reduction interventions among healthcare workers include social contact with peers or service users.^{36,38} However, this research is still in early phases^{36,38} with the impact of these interventions on patient-level care outcomes rarely examined.³⁶

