2.3 Adapting Training for the Stepped-Wedge Pilot Trial

Based on the findings of the initial training, we will adapt the training for a larger pilot test. We will use a randomized, hybrid Type 2 effectiveness-implementation design¹ to compare the adapted CHW training to usual CHW training (treatment as usual; TAU) in this setting. This type of design builds evidence for the effectiveness of an intervention in a real-world context, while also supporting the transition to implementation for subsequent, larger trials, with an equal emphasis on effectiveness and implementation.

This hybrid Type 2 effectiveness-implementation study will utilize a stepped wedge design to maximize power and ethically ensure that all clinics receive the CHW training, while also including a rigorous comparison condition. In this pilot trial, all clinics will receive the CHW training; each clinic will be randomized to the timing in which their CHWs receive the training.

Before CHWs receive this adapted training, they will receive TAU. In TAU, a CHW is typically deployed to a patient's home who has TB/HIV and has been LTFU for TB and/or HIV treatment with the central goal for supporting re-engagement in TB/HIV care. The CHW Typically goes to the patient's home twice per week for one month, or until the patient has re-engaged in care (if less than one month). CHWs typically meet with supervisors weekly for monitoring, which is limited to target review and does not include additional skills training or psychosocial debriefing. CHWs typically routinely document their visits to facilitate supervision and monitoring, and as part of efforts to roll out screening for depression and SU.

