NGO leader and stakeholder perceptions of feasibility and acceptability: Following the 6MFU assessment timepoint and collection of mixed-methods feasibility and acceptability data from CHWs, we will conduct qualitative interviews with leadership staff from NGOs, as well as policymakers and other stakeholders. These interviews will explore their perceptions of the feasibility and acceptability of the stepped-wedge training and aid in interpretation of data from CHWs themselves. Further, understanding organizational and systems barriers and facilitators to this training has important implications for longer term sustainment.

Patient Re-Engagement.

Chart Extraction. Chart extraction will be used to examine the rate of patient re-engagement in TB/HIV care. Specifically, data will be extracted from a centralized database of routinely collected data (*the Western Cape Province's Health Data Center*), which is hosted within the Western Cape Department of Health. The database includes information pertaining to demographic information, TB and HIV status, including whether TB and/or HIV treatment was initiated, date of initial diagnosis, lost-to-follow-up for TB and/or HIV care (i.e., missed treatment for two consecutive months), and date of TB and/or HIV treatment visits. This data is available by site and by unique patient health identification number (PHIN).

Around the time of a group's training, trained study researchers will receive a list of PHINs assigned to each CHW in the group in the past six-months from CHW supervisors/ workers overseeing CHWs. Aggregating data by CHW, and only viewing patients' PHIN and TB/HIV attendance data, we will extract whether patients re-engage, the time to re-engagement among those who return to care, and where patient re-engage in the six-months before the training.

Approximately six-months after a group's training, trained study researchers will receive a list of PHINs assigned to each CHW in the group since the training. Aggregating data by CHW, and only viewing patients' PHIN and TB/HIV attendance data, we will extract whether patients re-engage, the time to re-engagement among those who return to care, and where patient re-engage in the six-months before the training.

As only aggregate, de-identified data will be extracted from a centralized database, patients will not need to give informed consent.

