4.4 Secondary Preliminary Effectiveness Outcomes (Stepped-Wedge Trial Only)

4.4.1 Stepped-Wedge Trial

Re-engagement in TB/HIV care. The rate of patient re-engagement at the CHW level and time to re-engagement in TB/HIV care at the patient level in the six months prior to the CHW training compared to six-months following the CHW training will be evaluated using chart extraction. We will apply a Poisson regression model to compare rates of patient re-engagement at the CHW level, accounting for both clinic random effect and the fixed effect of time in the stepped wedge design. Pre-intervention patient re-engagement rates will be collected during the TAU phase for each clinic over the six months prior to the first CHW training, and post-intervention rates will be collected six months after the CHW training is complete via chart review. A Wald test will be used to test the effect of the CHW training intervention on the rates of patient re-engagement.

Time to re-engagement. To further investigate whether the CHW training intervention decreases patient time to re-engagement in TB/HIV care over six months, we will use a Cox Proportional Hazard survival model to model the patient-level outcome of time of re-engagement. Right censoring (those who do not re-engage within six months) is handled in the Cox model. A frailty model includes the random effect of clinics to account for unobserved heterogeneity. If the proportional hazard assumption is not met, the parametric accelerated failure time model can be used instead. We will control for amount of CHW contact with the patient (i.e., whether the CHW makes contact with the patient and the number of times the CHW visits the patient before the patient re-engages) and the patient's screening results (i.e., whether they screen positive for depression, hazardous alcohol use, and/or other drug use).

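### The Cox model for time to re-engagement adjusts for CHW contact and for a visit count that re-engagement itself cuts short, so its hazard ratio is not the total training effect

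*Combined protocol and SAP*

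**What the plan says.** Section 4.4.1 gives the purpose of the Cox model as "To further investigate whether the CHW training intervention decreases patient time to re-engagement in TB/HIV care over six months". It specifies a clinic frailty and censoring at six months, with an accelerated failure time (AFT) model as fallback if hazards are not proportional. It then adds: "We will control for amount of CHW contact with the patient". This is defined as whether contact is made and "the number of times the CHW visits the patient before the patient re-engages". The patient's depression and substance-use screening results are also adjusted for. The section does not say whether the visit count is one final total or a running count. It states no version of the model without these covariates.

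Section 2.3 describes usual visiting as typically "twice per week for one month, or until the patient has re-engaged in care", if that comes sooner than a month. Section 2.1 reports that "when CHWs have negative attitudes towards patients with depression or SU, they spend less time with these patients".

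**The concern.** There are two separate problems.

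1. **The outcome truncates the covariate.** A patient who returns in month 1 has few visits because visiting stopped on return. A final total entered as a fixed covariate uses information from after the time at which the hazard is being modelled. For patients who never return, a count of visits before re-engagement is not defined as worded.
2. **The covariates may lie on the causal path.** For patients assigned after training, contact and visiting are CHW behaviour that training could change. The support in section 2.1 is indirect, since it concerns time spent and not number of visits. If training does work partly through contact, adjusting for contact removes that part of the effect.

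Either way, the adjusted HR does not answer the question in 4.4.1. The most troubling case is a false benefit: CHWs complete more visits after training, patients return no sooner, and the model reports faster re-engagement. Section 5.3.2 ties scale-up partly to promoting re-engagement.

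**Working it through.** **Nothing to reproduce.** The plan states no hazard ratio, event count or power for this outcome. The check is therefore whether the planned adjustment recovers a known effect.

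**Inputs from the documents.** Two visits a week for about four weeks gives 2 × 4 = 8 scheduled visits, stopped by re-engagement (2.3). Follow-up is six months (4.4.1). There are 60 CHWs at about 20 per cluster (3.2.2), hence 60 / 20 = 3 clinics.

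**Assumed inputs.** 600 patients; 50-60% re-engaged by six months under TAU; 5, 10, 20 or 40% re-engaging in month 1; 70-80% of scheduled visits completed; visits themselves have no effect on return.

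**Why the count misleads.** A patient still out of care at one month has an expected count of 8 × 0.70 = 5.6. One who returns after a week has at most 2 scheduled visits, expected 2 × 0.70 = 1.4. A low count therefore marks early return. If completion rises to 80% after training, the first figure becomes 8 × 0.80 = 6.4. At an equal count, the trained patient is then more likely to be one whose visits were cut short by returning, and the model credits training with the difference.

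**Simulation 1: total visit count.** Return times are piecewise exponential, with a hazard change at week 4 and censoring at week 26. The clinic SD is 0.2 on the log hazard. The fitted model is h(t) = h0(t) × exp(βA + γV + clinic), where A is training and V the final count, with clinic as a fixed factor in place of the frailty. There were 500 replicates per scenario, so the Monte Carlo SE of a percentage is at most √(0.25/500) = 2.2 points.

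| Scenario | 5% early | 10% | 20% | 40% |
|---|---|---|---|---|
| (a) True HR 1.5, completion 70% throughout: adjusted HR | 1.50 | 1.50 | 1.46 | 1.36 |
| (a) power | 96% | 96% | 89% | 80% |
| (b) True HR 1.0, completion 70% to 80%: adjusted HR | 1.18 | 1.35 | 1.62 | 1.78 |
| (b) false significant benefit (nominal 2.5%) | 28% | 67% | 96% | 99% |
| (b) with CHW variation (SD 15 points): adjusted HR | 1.10 | 1.19 | 1.35 | 1.46 |
| (b) with CHW variation: false benefit | 11% | 32% | 67% | 90% |
| (c) True HR 1.5, completion 80% to 70%: adjusted HR | 1.27 | 1.09 | 0.88 | 0.76 |
| (c) with CHW variation: adjusted HR | 1.38 | 1.27 | 1.10 | 0.94 |

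Without the count, the model gave 0.99-1.01 for true HR 1.0 and 1.48-1.51 for true HR 1.5; power in (a) was 96-98%.

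**Running count instead of total** (80 replicates). With visits so far as a time-dependent covariate, scenario (b) gave 0.99 at both 10% and 40% early return, against 1.35 and 1.77 with the total. True HR 1.5 gave 1.50, against 1.36. The distortion in simulation 1 therefore comes from using the final total.

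**Simulation 2: contact and count together.** 40,000 patients per run, half trained, 182-day follow-up. Assumed: baseline hazard 0.003, 0.006 or 0.012 per day; 60% contacted; contact triples the hazard; no clinic or period effects. Ranges are over the three baseline hazards.

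| Scenario | HR, neither covariate | HR, both covariates |
|---|---|---|
| Training changes nothing | 1.00 | 0.99-1.01 |
| HR 1.5 given contact, same visiting | 1.38-1.43 | 1.24-1.41 |
| Effect only through contact (60% to 80%) | 1.21-1.24 | 0.99-1.01 |
| HR 1.5 plus contact 60% to 80% | 1.72-1.77 | 1.21-1.38 |
| No effect on return; visits rise from 2 to 2.5 or 3 a week | 0.98-1.01 | 1.87-4.96 |
| No effect on return; visits fall from 2 to 1.5 a week | 0.99-1.00 | 0.25-0.47 |

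In the second row, the unadjusted HR is below 1.5 because it averages over contacted and uncontacted patients. In the third row, adjusting for contact alone already gives 0.99-1.01: the whole effect is removed.

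**The case against.** Five points can be made for the plan.

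- **Another test of training exists.** The Poisson model of re-engagement rates in 4.4.1 names no contact or visit covariate. The Cox model is a further analysis under a secondary outcome in a pilot, and the primary SDS model is untouched. This stands and limits importance. It does not make the Cox HR answer its own question.
- **The figures need the count to be a final total.** A running count avoids the distortion. True, but 4.4.1 does not specify one, the total is the more natural reading, and a running count would still remove any effect that works through visits.
- **Visiting will vary between patients.** It will, especially among patients lost to follow-up. With a patient-level SD of 25 points (assumed; 100 replicates), scenario (b) shrinks to 1.03 / 1.08 / 1.14 / 1.28, with false benefit in 7 / 9 / 26 / 61%. A separate run gave about 1.06-1.30. The figures with uniform completion are therefore near the upper end for a 10-point change in completion. The bias shrinks but remains.
- **Nothing says training will change visiting.** Correct: it teaches stigma reduction, problem solving and motivational interviewing, and the schedule in 2.3 describes usual care. If visiting does not change, the distortion is small unless many patients return in month 1 (scenario (a)).
- **Size is driven by assumptions.** The null-case results for more visiting, 1.10-1.78 in simulation 1 and 1.87-4.96 in simulation 2, show this plainly. The contact result also rests on assumed values.

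**Conclusion.** The concern holds. As written, the adjusted HR is not the total effect of training on time to re-engagement, and the AFT fallback does not help if it keeps the same covariates.

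Confidence is high in the mechanism and low in any particular size. The error depends on two things the documents do not give: the share of patients returning in month 1, and whether training changes contact or visiting. The adjusted HR may be nearly unchanged, attenuated, reversed or inflated, so the simulations show what can happen and do not predict this trial. The problem should be fixed, but it is confined to this one secondary analysis.

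**What to change.** In 4.4.1, make the Cox (or AFT) model without contact and visit count the main analysis of the training effect. Adjust only for variables fixed before training can affect them. Keep the screening results only if they are recorded at or before assignment to the CHW, and state when that is. Report contact and visits as process outcomes, or in a separately labelled mediation or time-dependent analysis that uses visits so far and not the final total. Dropping the two covariates from the main model is a wording change; contact and visit data are still needed if they are reported as process outcomes.

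One separate item to settle at the same time: the chart-extraction text in 3.5.2g says "As only aggregate, de-identified data will be extracted from a centralized database" and describes extracting "the time to re-engagement among those who return to care", whereas 4.4.1 needs patient-level times and covariates, including for patients who do not return. These should be reconciled and the source of the contact, visit and screening data named. Section 2.3 suggests one: "CHWs typically routinely document their visits to facilitate supervision and monitoring". This step may need ethics review, because 3.5.2g rests the absence of patient consent on extracting only aggregate data.

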4.5 Missing Data (Stepped Wedge Trial Only)

Intent-to-treat (ITT) analysis will be conducted so all participants are analyzed based on their initial randomization assignments. All data will be included, regardless of subsequent participant dropout or missing data. For observed missing data, we will follow guidelines for handling clinical trial missing data. Specifically, data are assumed missing at random (MAR) for ITT analysis, but subsequent sensitivity analyses will be conducted where data are assumed not missing at random (MNAR) using multiple imputation to assess the robustness of the MAR assumption.

5. Ethical Considerations

5.1 Potential Risks to Participants

There is minimal risk from the research procedures in the present study. However, the following risks are still possible:

5.1.1 Breach to Confidentiality

As with any study, breach of confidentiality is a potential risk. Ways to minimize this risk are described below.

5.1.2 Psychological or Mental Discomfort

It is possible that participants will feel uncomfortable discussing certain topics in the interviews. For instance, patient participants may feel uncomfortable discussing their SU, feelings of depression, or experiences feeling stigmatised, and CHW participants may feel uncomfortable talking about their stigmatising behaviours.

5.1.3 COVID-19 Transmission

Due to the current COVID-19 pandemic, there is a potential risk for COVID-19 transmission between project staff and participants. Efforts to minimize these risks are described below.

5.2 Protections Against Risks

Every effort will be made to minimize all study-related risks. These efforts include:

5.2.1 Informed Consent

All CHWs and patients who are asked questions will complete informed consent procedures. To join the study, these participants must fully understand and sign the consent. All participants will have as much time as they want to review the consent form and ask questions. A study team member will also review the form with each participant. The consent form will include all study procedures, information about potential risks and benefits of participation, and information regarding whom they can contact for further questions. It will also state that participation is voluntary, that participants can refuse to answer any question, that participants can withdraw from the study at any time, and that participation (or lack thereof) is in no way related to their employment or care. All procedures and protocols will be approved by the South African Medical Research Council's (SAMRC) Human Research Ethics Committee (HREC) before study initiation.

Ensuring capacity to provide consent if a person has depression or uses substances.

Depression is considered a common mental disorder, and unlike severe mental illnesses such as schizophrenia, is unlikely to impact on a person's capacity to provide consent. The majority of people who screen positive on the screening tools we propose using will have mild to moderate psychological distress. In and of itself, this is unlikely to impact on capacity to provide consent. Ensuring that people are not intoxicated at the time of providing consent is important. If a potential participant appears acutely intoxicated, that person will not be consented into the study. We include a question about alcohol and other drug use in the past four hours, which would cause acute intoxication. Individuals who respond positively to this question will not be enrolled. Likewise, individuals who respond positively to this question before the interview will not be interviewed at that time. The

study team will also be trained by Drs [name] and [name] on how to detect simple signs of intoxication, such as impaired or slurred speech, smelling of alcohol, impaired coordination or balance—if any of these signs are present we will not enrol a participant or continue with any research activities at subsequent appointments with those already enrolled in the study. To increase our confidence in potential participant's capacity to consent, we include a simple assessment of capacity to provide consent in our consent form, that has been used in other studies with populations of patients who use alcohol and local studies with people with severe mental illness. These procedures were approved and used in the formative work to develop the training programme (#EC039-9/2020).

5.2.2 Preventing Breaches to Confidentiality

The confidentiality of each participant will be respected and maintained. Participant confidentiality will be ensured at all stages of the study.

All data will be kept confidential and only accessible to study staff. Participants' data will be identified by a study identification (ID) number only and a link between the names and ID numbers will be kept separately on a secure server and in a password protected document. This link will be destroyed after the study, including data analysis, has ended. The only individuals who have access to the link are the trained research staff in South Africa. Participant documents which include personal identifiers (such as signed consent forms) will be kept in locked files at SAMRC with restricted access. All other de-identified study documents will be kept in a secure location (such as UMD Box) and only study team members will have access to this location.

As part of the informed consent process, all participants will be advised that they may decline to answer any study questions. All study personnel working on the project will receive training about strictly adhering to study protocols regarding participant confidentiality.

Roleplays (and patient sessions in the Initial Pilot Training) will be recorded for analysis. The purpose of recording roleplays will be explained to all CHW participants in the informed consent process and authorization for recording will be obtained. Digital recordings will be uploaded to a secure database using the study computer immediately following the session and the audio file will be deleted from the digital recorder. Computer audio and video files will be saved in a secure location that only study-staff can access (i.e., UMD Box) and saved with a study ID. Any potentially identifying information will be removed or anonymized in the body of the written transcripts (e.g., the names of people). Following the South African good clinical practice (GCP) guidelines and guidelines set by the American Psychological Association (APA; APA Record Keeping Guidelines, Guideline #7), recordings will be maintained until seven years after the publication of the study. We will keep recordings even after transcription has occurred as a back-up and to allow for more nuanced coding if needed (e.g., of tone in addition to language). The ethics committee will review study procedures at least annually to review procedures pertaining to participant confidentiality.

English audio files may be transcribed to written text using Otter.ai by AI-Sense. All audio files sent to Otter.ai will be de-identified and saved only using participant ID numbers in order to protect participants' confidentiality. Team members will only use Otter.ai for assistance; they will still check and correct any errors in the transcripts from the service. Otter.ai uses artificial intelligence technology and syncs data over an encrypted

connection and stores it in a secure data centre that has both physical and electronic security. When the user deletes the recording, there will be no record retained by AI-Sense.

